2.1.2 Secondary

- To characterize the safety and preliminary efficacy of using localized UCA inertial cavitation to improve tumoral response to radioembolization.
- To determine if CEUS estimated tumor perfusion and residual vascularity 7-14 days post treatment can predict tumoral response to radioembolization.
- To evaluate tumoral response using the patient's 1 month MRI (obtained clinically) and determine the accuracy of MR or CT tumor evaluation at this earlier time point.

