3.6.2 Study Completion

Study completion and publication of results is anticipated in July of 2025

4 Study Enrollment and Withdrawal

Patients at least 18 years of age, medically stable who have a previously untreated intrahepatic non-HCC tumor greater than 1 cm but small enough to be visualized in the ultrasound 3D volume will be included. These patients will be recruited from the Hepatology department, Interventional Radiology, and the Multidisciplinary Liver Tumor Board of the Kimmel Cancer Center at Thomas Jefferson University.

A sufficient number of patients will be screened in order to enroll 20 patients with non-HCC tumors receiving TARE over the duration of the study.

Patients who are discontinued from the study prior to the completion of all planned procedures and assessments will not be replaced.

Each subject is identified in the study by a unique subject number that is assigned when subject enrolls after signing the Informed Consent Form. Once assigned the subject number cannot be reused for any other subject. The same primary identifier will be used throughout the study.

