11.1 Study Hypotheses

H1: Contrast reperfusion time, degree of tumor enhancement relative to the surrounding parenchyma, tumoral IFP and 3D morphological features of the vasculature quantified via CEUS before therapy correlate with SoC mRECIST reads of non-HCC tumor patients treated with TARE.

H2: mRECIST reads for non-HCC tumor patients receiving TARE combined with microbubble inertial cavitation have more complete response (CR) and partial response (PR) reads compared to the historical group treated with TARE alone.

H3: Patient's time to required next treatment and overall survival are longer for non-HCC tumor patients receiving TARE combined with microbubble inertial cavitation compared to the historical group treated with TARE alone.

H4: Observed and self-reported adverse events, and changes in liver function tests (LFTs) one month post-TARE in non-HCC tumor patients receiving TARE combined with microbubble inertial cavitation are similar compared to the historical group treated with TARE alone.

H5: Values of tumor perfusion and residual vascularity quantified by CEUS 2-4 hours, 1 week, and 2 weeks after TARE therapy are lower in CR and PR mRECIST reads of non-HCC tumor patients treated with TARE.

H6: Reductions of tumor perfusion and residual vascularity values quantified by CEUS 2-4 hours, 1 week, and 2 weeks after TARE therapy are more frequent in CR and PR mRECIST reads of non-HCC tumor patients treated with TARE.

H7: Tumoral response in mRECIST reads of MRI or CT (obtained clinically from patients treated with TARE) at 1 month post treatment will agree with response in their mRECIST reads at 3-6 months.

H8: Values of IFP quantified by SHAPE 2-4 hours, 1 week, and 2 weeks after TARE therapy are lower in CR and PR mRECIST reads of patients treated with TARE.

H9: Reductions of IFP values quantified by SHAPE 2-4 hours, 1 week, and 2 weeks after TARE therapy are more frequent in CR and PR mRECIST reads of patients treated with TARE.

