11.2 Analysis Plans

In general, categorical data will be summarized as counts and percentages (or proportions) and continuous data will be summarized with descriptive statistics such as mean, standard deviation (SD), median, and range. All statistical analysis will be performed by [name] using SAS version 9.4 (Cary, NC). All statistical tests will be conducted at a nominal $\alpha=0.05$ level. For H1 (see Section 11.1 above), the respective relationships between the CEUS-derived contrast reperfusion time, degree of tumor enhancement relative to the surrounding parenchyma, tumoral IFP and 3D morphological features of the vasculature with the patients' subsequent mRECIST diagnosis (3 levels: stable disease, partial response, or complete response) will be evaluated by testing for mean difference in the CEUS measures between response levels by analysis of variance (ANOVA). Historical controls ($n=20$) will be identified from a pool of recently treated non-HCC patients at Jefferson that meet study eligibility criteria for the study and match our enrollees by propensity score based on a logistic regression model including patient age, tumor size, bilirubin and ECOG performance score and utilizing a greedy matching algorithm. Testing for the effect of radioembolization on tumor response in H2 will be conducted using non-parametric Mann-Whitney U-tests of the differences in mRECIST distributions between historical controls and enrolled patients. The difference in time-to-event endpoints (i.e., to next treatment or death, respectively) between the treated and historical control patients for H3 will be estimated and tested using Kaplan-Meier survival methods and log-rank tests. Differences in safety data will be evaluated for H4 with descriptive statistics, but not statistical hypothesis tests. A similar ANOVA approach taken for evaluating H1 will be taken for evaluating the means of CEUS measures at different times (2-4 hours, 1 week, and 2 week, respectively) of tumor perfusion and residual vascularity values between response levels to address H5 and SHAPE IFP values for addressing H8, as well as the means of changes from baseline in these measure for addressing H6 and H9. The agreement on response between mRECIST response diagnoses at 1 month and 3-6 months post-TARE will be tested using McNemar's test.

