11.3.2 Efficacy Review

The primary measure of tumor response will be evaluated using mRECIST criteria as determined by [name] and [name] in consensus using 3-6 month contrast enhanced MRI or CT (blinded to patient group). Following a wait period and randomization of the patient order, both readers will also evaluate tumoral response using the patient’s 1 month MRI (obtained clinically) to determine the accuracy of MR or CT tumor evaluation at this earlier time point and its use as an alternative to CEUS. Finally, each patient’s time to required next treatment and overall survival will be monitored, although this is a secondary outcome for this study and expected to surpass the timeline of this study.

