11.4 Sample Size Considerations

Sample size for this pilot study is primarily driven by patient availability and larger, multi-center randomized trials will likely be needed to fully demonstrate efficacy. However, for the primary objective, a sample size of 20 patients (of which we expect 25% having stable disease, 50% partial responders, and 25% complete responders) will provide 80% power to detect a 0.76 standard deviation difference in CEUS measurement means (e.g., mean contrast perfusion time) between mRECIST response levels, by analysis of variance (ANOVA) with a nominal 5% type I error rate. Similarly, in analyses comparing the prospective treated patients to matched historical control patients, 20 patients per arm will provide 80% power to detect a relative effect size of 0.66 standard deviations by t-test with a nominal 5% type I error rate (i.e., a moderately large, but reasonable effect given our current data in HCC patients).

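### McNemar's test, the only test named for H7, measures neither the agreement nor the accuracy of the 1-month mRECIST read

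*Combined protocol and SAP*

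**What the plan says.** The question appears in three places in the combined protocol and SAP. H7 in section 11.1 states that response on clinical MRI or CT "at 1 month post treatment will agree with response in their mRECIST reads at 3-6 months". The third secondary objective in section 2.1.2 is to use the 1-month scan and "determine the accuracy of MR or CT tumor evaluation at this earlier time point". Section 11.3.2 has both readers return to the 1-month images "to determine the accuracy of MR or CT tumor evaluation at this earlier time point and its use as an alternative to CEUS".

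The method appears once, in the last sentence of section 11.2: "The agreement on response between mRECIST response diagnoses at 1 month and 3-6 months post-TARE will be tested using McNemar's test". No kappa, percent agreement, sensitivity, specificity, predictive value, confidence interval or agreement threshold is named for this question. Section 11.4 gives H7 no target and no power. Section 11.2 opens with a general rule that categorical variables are reported as counts with percentages; it does not mention paired reads.

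**The concern.** H7 and the objective are about individual patients: does the early read put each patient where the later read will put that patient, and how often is it wrong? McNemar's null hypothesis concerns the group: the proportion of responders is equal at the two times. Patients misclassified in opposite directions cancel out.

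The direction of inference is also awkward. H7 predicts agreement, which is not the test's alternative hypothesis. A significant result shows a shift in response rate. A non-significant result shows neither agreement nor disagreement. Nowhere does the plan say that p >= 0.05 will be read as agreement, but naming this test as the test of agreement invites that reading.

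At stake is the conclusion on whether 1-month imaging could stand in for CEUS. As written, the named analysis cannot supply it, and any agreement or accuracy measure added later would be chosen after the data are seen.

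**Working it through.** The plan gives no figure for H7, so there is none to reproduce. The check compares what the test returns with what H7 asks.

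**Inputs**
- Pairs of reads: 20 at most (sections 3.2 and 4).
- Response at 3-6 months: 75%, i.e. 15 responders and 5 non-responders, from section 11.4 ("of which we expect 25% having stable disease, 50% partial responders, and 25% complete responders").
- Response at 1 month: not given, so a range of 40% to 75% is used.
- Alpha 0.05 (section 11.2). Two-sided testing and the exact version are assumed, as neither is stated.
- Responder means CR or PR. This is assumed for H7: McNemar's test needs two categories, while section 11.2 uses three levels for H1.

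**Formulas.** Let a = responder at both times, b = responder at 3-6 months only, c = responder at 1 month only, d = responder at neither.
- Exact McNemar: p = min(1, 2 × P(X ≤ min(b, c))), with X ~ Binomial(b + c, 1/2).
- Agreement: po = (a + d)/20.
- Kappa = (po − pe)/(1 − pe), with pe = [(a + b)(a + c) + (c + d)(b + d)]/400.
- Against the 3-6 month read: sensitivity = a/(a + b), specificity = d/(c + d).

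**Step 1: example tables, each with 15 later responders**

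| a/b/c/d | Agreement | Kappa | Sensitivity | Specificity | Exact p |
|---|---|---|---|---|---|
| 10/5/5/0 | 50% | -0.33 | 67% | 0% | 1.0 |
| 14/1/1/4 | 90% | 0.73 | 93% | 80% | 1.0 |
| 15/0/0/5 | 100% | 1.00 | 100% | 100% | 1.0 |
| 9/6/0/5 | 70% | 0.43 | 60% | 100% | 0.031 |

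For the first row, pe = (15 × 15 + 5 × 5)/400 = 0.625 and kappa = (0.50 − 0.625)/0.375 = -0.33. For the last, p = 2 × (1/2)^6 = 0.031. The first row is an extreme counterexample, not an expected result. The only table rejected is one with better agreement than the first row.

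**Step 2: how often an uninformative early read gives p >= 0.05.** Take the 1-month read as independent of the later one, with response rate r. The discordant probabilities are 0.75(1 − r) for b and 0.25r for c. Summing the multinomial probabilities over all (b, c) with p >= 0.05 gives:

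| 1-month rate r | Expected agreement | Non-significant, exact | Non-significant, uncorrected chi-square |
|---|---|---|---|
| 75% | 62.5% | 98.2% | 95.5% |
| 70% | 60% | 97.4% | 94.4% |
| 60% | 55% | 90.8% | 85.2% |
| 50% | 50% | 75.7% | 66.9% |
| 40% | 45% | 52.9% | 42.7% |

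The result is driven by how far the two response rates differ, not by whether the reads match patient by patient; kappa is expected to be zero in every row.

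**Step 3: what direct estimates would give with 20 pairs (exact 95% CIs).** Agreement 18/20 = 90% (68% to 99%). Sensitivity 14/15 = 93% (68% to 99.8%). Specificity 4/5 = 80% (28% to 99.5%), or 5/5 = 100% (48% to 100%). For 14/1/1/4, kappa 0.73 has an asymptotic interval of 0.39 to 1.0 (truncated).

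**The case against.** Five points can be made for the plan.

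- **The descriptive rule could already yield a cross-table.** Counts and percentages are promised for categorical data. That is compatible with a paired table, but the rule commits to no paired table and names no agreement or accuracy measure, while H7 is assigned to McNemar's test by name. It softens the gap without closing it.
- **The test is not uninformative.** Equal response rates are necessary for full agreement, so a significant result can contradict H7, for example if many patients respond late. This stands, and is why the test is worth keeping as a supplement. It can count against H7 but cannot establish it.
- **The percentages rest on chosen inputs.** Independence is a deliberate worst case: the same lesions are read by the same two readers. Section 1.1 also quotes 25-60% response for TARE, which would mean 8 to 15 non-responders of 20 rather than 5. If historical controls entered H7 (40 pairs, assumed), the 50% and 40% rows would fall to about 45% and 16%. With equal rates the figure stays near 97%. These points limit the percentages to illustration; the identical p-values in Step 1 do not depend on them.
- **Kappa is imprecise and depends on prevalence.** True with 20 pairs. Percent agreement with sensitivity and specificity would meet the need; kappa is an addition.
- **The consequence is limited.** This is a secondary objective of a pilot, the primary analysis is untouched, and the paired reads remain available for later estimates. What is lost is prespecification.

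**Conclusion.** The concern holds. The method named for H7 does not address the question that H7, section 2.1.2 and section 11.3.2 pose. Poor, good and perfect patient-level agreement can all return p = 1.0. Under independent reads with 20 patients and 75% later response, an uninformative early read would be non-significant in 98% of trials at an equal 1-month rate, down to 53% at a 1-month rate of 40%. Those percentages depend on the assumed rates, independence and the exact test; the mismatch between test and question does not. This should be fixed, but it does not threaten the trial: it affects one secondary objective, and the data needed are already planned.

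**What to change.** In section 11.2, replace McNemar's test as the H7 analysis with:

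1. The paired 1-month by 3-6 month cross-table, stating the responder definition (CR or PR versus not) and whether only the 20 enrollees or also the historical controls are included.
2. Percent agreement and kappa for responder status, each with a 95% CI. Weighted kappa on the ordered mRECIST categories, with progressive disease if observed, is a useful addition.
3. Sensitivity and specificity of the 1-month responder read against the 3-6 month read, with exact 95% CIs.

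Present these as estimates, not as a pass/fail test, and say that specificity would rest on about 5 non-responders under the section 11.4 split. Keep McNemar's test, in its exact form, only as a supplementary check for a systematic shift in response rate, and state that a non-significant result is not evidence of agreement.

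The cost is plan wording and a few lines of analysis code. No new data, scans or readers are needed.

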11.3 Interim Analyses and Stopping Rules

This is a pilot study, no interim analysis will be considered.

11.3.1 Safety Review

Safety outcomes will be compared between the treatment group and the historical group using observed and self-reported adverse events, and changes in LFTs one month post-embolization (performed as part of clinical standard of care). LFTs will include blood tests for alanine aminotransferase, alkaline phosphatase, aspartate aminotransferase, bilirubin, albumin, total protein, and prothrombin time. SPECT imaging will be evaluated for all patients by two blinded radiologists to evaluate if the initial UTMD session skews microsphere distribution in the liver.

11.3.2 Efficacy Review

The primary measure of tumor response will be evaluated using mRECIST criteria as determined by [name] and [name] in consensus using 3-6 month contrast enhanced MRI or CT (blinded to patient group). Following a wait period and randomization of the patient order, both readers will also evaluate tumoral response using the patient’s 1 month MRI (obtained clinically) to determine the accuracy of MR or CT tumor evaluation at this earlier time point and its use as an alternative to CEUS. Finally, each patient’s time to required next treatment and overall survival will be monitored, although this is a secondary outcome for this study and expected to surpass the timeline of this study.

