Study Summary

Title:	Contrast-Enhanced Ultrasound for Diagnosis and Therapy of Cholangiocarcinoma
Précis:	20 patients with biopsy-proven intrahepatic cholangiocarcinoma (ICC) or other non-HCC tumors in the liver will receive their standard of care (SoC) sub-lobar transarterial radioembolization (TARE), in addition to four sessions of ultrasound contrast infusion and ultrasound scanning. One session will be within 1 month prior to treatment and the other three will be at different time points after treatment. The treatment outcomes will be compared to a historical group of similar patients receiving TARE alone. The main hypotheses are that contrast-enhanced ultrasound (CEUS) can be used to predict non-HCC response to TARE prior to therapy, improve the sensitivity of these tumors to radiotherapy, and assess treatment response earlier than the current clinical standard.
Objectives:	To evaluate the utility of CEUS-derived quantitative measures in predicting tumor response before and in the early phases after TARE treatment, and to evaluate the safety and efficacy of microbubble cavitation in improving TARE treatment.
	Primary: 
• To determine the ability of quantitative volumetric CEUS to predict tumoral response to TARE prior to therapy.
	Secondary: 
• To characterize the safety and preliminary efficacy of using localized UCA inertial cavitation to improve non-HCC tumor response to radioembolization.• To determine if CEUS estimated tumor perfusion and residual vascularity can predict non-HCC tumor response to radioembolization 7-14 days post treatment.• To evaluate tumoral response using the patient's 1 month MRI (obtained clinically) and determine the accuracy of MR or CT tumor evaluation at this earlier time point.
	Exploratory: 
• To examine the utility of SHAPE to noninvasively monitor tumoral interstitial fluid pressure (IFP) and provide an early biomarker of radiotherapy response.
Population:	20 patients with intrahepatic cholangiocarcinoma (ICC) or other non-HCC tumors receiving sub-lobar transarterial radioembolization

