2.1 Objectives

To evaluate the utility of CEUS in prediction of tumoral response to TARE prior to therapy, improving the sensitivity of non-HCC tumors to radiotherapy, and assessment of treatment response earlier than the current clinical standard.

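### The 1-month scan is to be judged as an alternative to CEUS, but no planned analysis compares the two early tests, and McNemar's test does not measure the scan's accuracy

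*Combined protocol and SAP*

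**What the plan says.** Section 11.3.2 gives the reason for reading the 1-month scan: "to determine the accuracy of MR or CT tumor evaluation at this earlier time point and its use as an alternative to CEUS". The matching objective in Section 2.1.2 concerns the accuracy of early MR or CT. H7 in Section 11.1 turns this into a statement that response "at 1 month post treatment will agree with response in their mRECIST reads at 3-6 months".

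For early CEUS, Section 2.1.2 has the objective "To determine if CEUS estimated tumor perfusion and residual vascularity 7-14 days post treatment can predict tumoral response to radioembolization". Section 11.2 then says "A similar ANOVA approach taken for evaluating H1 will be taken for evaluating the means of CEUS measures at different times", which covers H5 and, for changes from baseline, H6. For the scan it says "The agreement on response between mRECIST response diagnoses at 1 month and 3-6 months post-TARE will be tested" with McNemar's test.

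The Précis lists among the main hypotheses that CEUS can "assess treatment response earlier than the current clinical standard", and Section 2.1 repeats this as an objective: "assessment of treatment response earlier than the current clinical standard".

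None of H1 to H9, the endpoints in Section 2.2, the analyses in Section 11.2 or the exploratory analysis in Section 11.5 compares CEUS with the 1-month scan. No CEUS cut-off, response call, sensitivity, specificity or AUC is defined.

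**The concern.** Whether one early test can stand in for another is a comparative question. It needs both tests on a common scale, against the same reference, in the same patients. The reference (3-6 month mRECIST) and the patients are common to both. The scale is not: one analysis yields differences in CEUS means and the other a p-value for a change in the overall response rate.

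Two things are at stake. First, the trial could end without an answer to a purpose it states, although it collects the data. Second, if the comparison is improvised once results are known, CEUS offers several measures, times and forms to choose from, and picking the best in 20 patients would flatter it.

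**Working it through.** The plan gives no sample size, power or margin for CEUS against the 1-month scan, so it has no figure to reproduce. Section 11.4 covers only the ANOVA and the comparison with historical controls.

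**Inputs from the plan.** There are 20 enrolled patients, with an expected 25% stable disease, 50% PR and 25% CR (Section 11.4). That is about 5 non-responders and 15 responders (CR or PR). Study CEUS takes place at about 1 and 2 weeks (Sections 3.3 and 5.8). Clinical MRI/CT is collected at about 1-2 months and 3-6 months (Section 1.3).

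**Step 1: does McNemar's test measure accuracy?** Take response as yes/no and set two hypothetical tables of the 1-month read against the 3-6 month read.

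| | Table A | Table B |
|---|---|---|
| Responder at both times | 11 | 9 |
| Responder at 1 month only | 4 | 0 |
| Responder at 3-6 months only | 4 | 6 |
| Non-responder at both times | 1 | 5 |
| Agreement | 12/20 = 60% | 14/20 = 70% |
| Sensitivity | 11/15 = 73% | 9/15 = 60% |
| Specificity | 1/5 = 20% | 5/5 = 100% |
| Exact McNemar p | 1.00 | 2 × 0.5^6 = 0.031 |

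- Kappa in A: chance agreement is (15×15 + 5×5)/400 = 0.625, so kappa = (0.60 - 0.625)/(1 - 0.625) = -0.07.
- Kappa in B: chance agreement is (9×15 + 11×5)/400 = 0.475, so kappa = (0.70 - 0.475)/(1 - 0.475) = 0.43.

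The test finds no difference in the table with worse-than-chance agreement and rejects in the better one. It uses only the two discordant counts, so its p-value does not estimate accuracy.

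**Step 2: can the planned outputs be set side by side?** H5/H6 give mean CEUS values, or changes, by response level. H7 gives the p-value above. Neither says what proportion of patients CEUS or the scan would classify correctly, so no difference between the tests can be formed from them.

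**Step 3: how precise would a comparison be?** The documents give no discordance rates, so these are assumptions. For a paired difference in accuracy, the 95% half-width is 1.96 × sqrt[(b + c - (b - c)²)/20], where b and c are the proportions discordant in each direction.

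- b = c = 0.05: 1.96 × sqrt(0.10/20) = 0.14.
- b = c = 0.15: 1.96 × sqrt(0.30/20) = 0.24.

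Exact two-sided McNemar power for a 20-point difference in accuracy is 20% with 5% discordant in the minority direction and 17% with 10%.

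The AUC recommended below is a different quantity, but it is limited by the same 5 non-responders. It is based on 5 × 15 = 75 responder/non-responder pairs. One non-responder enters 15 of them, so a single patient can move the AUC by up to 15/75 = 0.20. For specificity, 4/5 has an exact 95% CI of 28% to 99%.

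**Step 4: how many CEUS candidates are there?** Two quantities (perfusion, residual vascularity) × two times (1 and 2 weeks) × two forms (value, change from baseline) = 8, before choosing how each quantity is computed.

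**The case against.** **The comparison rests on one clause.** It appears only in Section 11.3.2, and no objective, hypothesis or endpoint promises a direct contrast. This stands, and it is why deleting the clause is an acceptable alternative. It does not remove the gap in accuracy: Section 2.1.2 also asks for the accuracy of the early scan, which McNemar's test does not supply.

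**This is a pilot sized by availability, and the comparison would have little power.** True, as Step 3 shows. Low power rules out a confirmatory test. It does not rule out an estimate with its interval, which is what Section 11.4's expectation of larger trials calls for.

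**A reader might infer that the main hypothesis of earlier assessment is left untested.** The documents do not support that. They pose it as a hypothesis and objective, not as an established fact, and do not say that the clinical standard is the 1-month scan. If the standard is the 3-6 month read, H5 and H6 partly address it by relating CEUS in the first two weeks to that read.

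**A reader might also infer that the 1- and 2-week CEUS exams are diagnostic extras gaining only about two weeks.** That is not supported either. Those visits also deliver the microbubble destruction under study. Section 1.3 puts the early scan at about 1-2 months. With 30-day months the lead runs from 30 - 14 = 16 days to 60 - 7 = 53 days, or about 2 to 7.5 weeks.

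**Conclusion.** The point holds in a limited form. Followed exactly, the plan cannot say whether the 1-month scan could be used in place of early CEUS, and McNemar's test does not give the scan's accuracy. This follows from the text and from what the two tests measure, not from any assumed rate.

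The example tables and discordance rates are illustrations. The count of about 5 non-responders is the plan's own expectation. The defect affects a secondary purpose and leaves the primary objective untouched. It is worth correcting because enrolled patients are already due to have both tests and the reference. The resulting estimate would be wide and could not establish that either test is superior or equivalent.

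**What to change.** In Section 11.2:

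1. Before the 3-6 month reads are available, name one CEUS measure, in one form (value or change), at one time point (7 or 14 days).
2. In patients with both exams, report the AUC (concordance) with 3-6 month CR/PR for that measure and for the 1-month mRECIST category, and the paired difference with a 95% CI.
3. Report sensitivity, specificity and the cross-table of the 1-month read against the 3-6 month read.
4. Label all of this as estimation only.
5. Report actual scan dates, since the early scan may fall anywhere from about 1 to 2 months.
6. State that the 1-month read shares criteria and readers with the reference, which favours it over CEUS. The wait period and re-ordering in Section 11.3.2 address recall, not the shared criteria.

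If the comparison is not added, delete the closing clause of the Section 11.3.2 sentence about using the scan in place of CEUS, and draw no conclusion about CEUS relative to the 1-month scan. Item 3 is still needed for the accuracy objective.

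The cost is SAP wording and a small amount of analysis, with no new data, visits or readers. The drawback is an imprecise estimate that must be reported as such.
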